**10) Provisions to Protect the Privacy Interests of Subjects**

Members of the research team will have access to data contained in medical records and data provided by the patients. Only authorized members of the research team will be able to access this information. The research study will be thoroughly explained to potential subjects in a private manner. Consenting will be done also in a private setting, away from other subjects.

**11) Compensation for Research-Related Injury**

There is no compensation for research-related injury in this study.

**12) Economic Burden to Subjects**

There will be no additional economic burden to subjects outside of the typical costs for treatment of chronic, non-healing, lower extremity wounds in the diabetic population.

Patients will attend bi-weekly visits with their provider, which is the current standard of care for patients meeting eligibility requirements of this study and is billable to insurance.

Study funds will cover an ECG, A1c lab, CMP, INR/PT, and/or lipid panel lab if needed at the time of enrollment.

The oral immunonutrition supplements will be covered by study funds and provided to subjects free of charge. Study funds will cover a CMP and a lipid panel (at 6-week timepoint or within 3 months of study completion) for study participants in the treatment arm.

If the final safety follow-up visit is an additional visit solely for the purposes of participating in the research study, then study funds will cover the cost of this visit.

### **13) Consent Process**

Subjects who meet eligibility criteria will be consented during their previously scheduled office visit by a participating provider. The study will be thoroughly explained to the subject and all questions/concerns will be addressed. Research team members will be available to assist if the patient agrees to participate with the surgeon. Signed consent documents will be stored in a locked office within Prisma Health Orthopedics and a copy will be uploaded to the subject's electronic medical record.

Subjects must speak English and understand instructions. Subjects that do not speak English will not be enrolled in this study. We will follow the IRB Written Documentation of Consent.

### **14) Process to Document Consent in Writing**

We will follow the IRB Written Documentation of Consent.

## **Appendix 1: Schedule of Events**

### **Visit 0: Previously scheduled office visit**

- Provider reviews study with patient, confirms that inclusion/exclusion criteria are met, and obtains informed consent
  - a. Note: If the patient has not had an ECG (within 3 months of study enrollment), a lipid panel (within 3 months of study enrollment), a CMP/INR/PT (within 3 months of study enrollment), and/or an A1c lab (within 6 months of study enrollment) these will be performed to confirm normal parameters prior to continuation of study activities. If any labs or ECG are required, results will be reviewed by the provider and the patient will resume study activities at their next scheduled visit.
- Provider documents characteristics of wound via PUSH Tool 3.0, obtains plantar pressure profile readings via Tekscan Pressure Mat, and captures clinical photos
- Provider verifies and documents concomitant medications.
- Provider visualizes and evaluates any additional wounds that are present and records characteristics in the patient's chart.
- Patient is randomized to receive either oral immunonutrition supplementation or standard care
- Patient is provided oral immunonutrition supplements and compliance log, if appropriate

### **Biweekly Office Visits**

- Document characteristics of wound via PUSH Tool 3.0, obtain pressure profile reading (visits 0 and week 6), capture clinical photos, obtain interval history, perform interval physical exam, verify and document concomitant medications, visualize and record characteristics of additional wounds present.
- Patient completes questionnaire (VAS, experienced symptoms since enrollment, review of supplement compliance (if applicable))

### **Biweekly Phone Calls**

- Patient completes questionnaire over phone with research coordinator (VAS, experienced symptoms since enrollment, review of supplement compliance (if applicable))

#### **Phone Call #1**

Week 1  
After 7 days of oral immunonutrition

#### **Office Visit 1**

Week 2  
After 14 days of oral immunonutrition

#### **Phone Call #2**

Week 3  
After 21 days of oral immunonutrition

#### **Office Visit 2**

Week 4  
After 28 days of oral immunonutrition

#### **Phone Call #3**

Week 5  
After 35 days of oral immunonutrition

#### **Office Visit 3**

Week 6/Completion visit

After 42 days of oral immunonutrition  
\*Patients in treatment arm return compliance log, complete satisfaction survey, and have lipid panel and CMP labs drawn (or within 3 months of study completion) \*

#### **Final Safety Follow-up Visit**

6-8 Weeks after Office Visit 3/discontinuation of supplement

## Appendix 2: PUSH Tool 3.0

### Pressure Ulcer Scale for Healing (PUSH) PUSH Tool 3.0

Patient Name \_\_\_\_\_ Patient ID# \_\_\_\_\_

Ulcer Location \_\_\_\_\_ Date \_\_\_\_\_

#### Directions:

Observe and measure the pressure ulcer. Categorize the ulcer with respect to surface area, exudate, and type of wound tissue. Record a sub-score for each of these ulcer characteristics. Add the sub-scores to obtain the total score. A comparison of total scores measured over time provides an indication of the improvement or deterioration in pressure ulcer healing.

LENGTH X WIDTH (in cm  )	0	1	2	3	4	5	Sub-score
	0	< 0.3	0.3 – 0.6	0.7 – 1.0	1.1 – 2.0	2.1 – 3.0	
EXUDATE AMOUNT	0	1	2	3	4	5	Sub-score
TISSUE TYPE	0	1	2	3	4	5	Sub-score
							TOTAL SCORE

**Length x Width:** Measure the greatest length (head to toe) and the greatest width (side to side) using a centimeter ruler. Multiply these two measurements (length x width) to obtain an estimate of surface area in square centimeters (cm^2). Caveat: Do not guess! Always use a centimeter ruler and always use the same method each time the ulcer is measured.

**Exudate Amount:** Estimate the amount of exudate (drainage) present after removal of the dressing and before applying any topical agent to the ulcer. Estimate the exudate (drainage) as none, light, moderate, or heavy.

**Tissue Type:** This refers to the types of tissue that are present in the wound (ulcer) bed. Score as a "4" if there is any necrotic tissue present. Score as a "3" if there is any amount of slough present and necrotic tissue is absent. Score as a "2" if the wound is clean and contains granulation tissue. A superficial wound that is reepithelializing is scored as a "1". When the wound is closed, score as a "0".

- 4 – Necrotic Tissue (Eschar):** black, brown, or tan tissue that adheres firmly to the wound bed or ulcer edges and may be either firmer or softer than surrounding skin.
- 3 – Slough:** yellow or white tissue that adheres to the ulcer bed in strings or thick clumps, or is mucinous.
- 2 – Granulation Tissue:** pink or beefy red tissue with a shiny, moist, granular appearance.
- 1 – Epithelial Tissue:** for superficial ulcers, new pink or shiny tissue (skin) that grows in from the edges or as islands on the ulcer surface.
- 0 – Closed/Resurfaced:** the wound is completely covered with epithelium (new skin).

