**e. Study Endpoints**

Primary Outcome: Complete wound closure of a chronic, non-healing wound at 6 weeks.

- a. Complete wound closure will be defined as skin reepithelialization without drainage or dressing requirements confirmed at two consecutive study visits 2 weeks apart. Incidence of complete wound closure in the control group will be compared to that of the treatment group.

Secondary Outcome: Rate of wound closure over 6-week study period.

- a. PUSH Tool 3.0 scores and clinical photos will be compared between the control group and treatment group to evaluate the rate of wound closure over the course of the 6-week study period.

Tertiary Outcome: Compliance and patient satisfaction with immunonutrition supplementation regimen.

- a. Patient satisfaction surveys and compliance logs will be evaluated to assess feasibility of implementing an immunonutrition regimen into standard wound care.

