  - a. If randomized to the control group (SOC only), patients will receive standard of care defined as sharps debridement, appropriate dressing, and offloading. If randomized to the treatment group (SOC + Immunonutrition), subjects will receive standard of care defined as sharps debridement, appropriate dressing, and offloading in addition to a 6-week supply of Omega-3 fatty acids (soft gel form, 2 pills per day, total of 1.68 grams) and L-Arginine/Vitamin C (powder form, to be mixed with 8 oz liquid, 1 scoop once daily, total of 4.5 grams L-arginine and 500 mg vitamin C). Subjects will also be provided a compliance log with detailed instructions for taking and tracking supplements.
5. Patients will be scheduled for biweekly wound checks with their provider (weeks 2, 4, 6). Wound characteristics will be documented at each follow up visit using the PUSH Tool 3.0, images of the wound will be obtained, and an interval history and physical exam will be documented. The provider will verify and document concomitant medications in the patient's chart. The provider will visualize and evaluate any additional wounds that are present (new or present at time of enrollment) and record characteristics in the patient's chart. Patients will complete a questionnaire detailing their pain level (VAS), symptoms experienced during the treatment phase, and any unscheduled visits to emergency departments/urgent care centers. This will be completed via a paper survey in clinic during their office visit (Appendix 4). On weeks where an office visit is not scheduled (weeks 1, 3, 5), a research coordinator will call the patient and collect survey responses (Appendix 3).
6. At the final office visit (week 6), plantar pressure profiles will be recorded via the Tekscan Pressure Mat, and clinical plantar weight-bearing images will be captured. Patients randomized to receive the oral immunonutrition supplementation will complete an additional survey detailing their satisfaction with the treatment plan and any additional thoughts they would like to share (Appendix 5) and return the completed compliance log

(Appendix 6). Patients in the treatment arm will have CMP and lipid panel labs drawn at this timepoint or within 3 months of study completion.

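### The secondary outcome, rate of wound closure, rests on PUSH scores whose total mixes wound condition with a coarsely banded size score; it should be defined on measured area.

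*Combined protocol and SAP*

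**What the plan says.** Section 6.e names the endpoint: "Secondary Outcome: Rate of wound closure over 6-week study period". It then gives the means of assessment: "PUSH Tool 3.0 scores and clinical photos will be compared between the control group and treatment group to evaluate the rate of wound closure". It does not say whether the total or a sub-score is meant, and it gives no rule for measuring the photographs.

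Appendix 2 has three items: length × width in bands, exudate amount and tissue type. The provider is told: "Add the sub-scores to obtain the total score". The comparison that the tool itself recommends is of totals: "A comparison of total scores measured over time provides an indication of the improvement or deterioration in pressure ulcer healing". For exudate the instruction is: "Estimate the exudate (drainage) as none, light, moderate, or heavy". Tissue runs from 4 (necrotic) through 3 (slough), 2 (clean, granulating) and 1 (reepithelializing) to 0 (closed). The graph in Appendix 2 runs from 17 down to 0.

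Under Section 6.f, the standard care common to both arms acts on the wound bed: "patients will receive standard of care defined as sharps debridement, appropriate dressing, and offloading".

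Section 6.h lists Cox regression for rate of closure without defining an event, and lists time to complete healing as a separate outcome. Its main model is for the proportion of wound closed, whose extreme values it describes in terms of reduction in wound size.

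**The concern.** The endpoint is called closure, but the score that feeds it also responds to how wet the wound is and what tissue lies in its bed. In an open wound both can improve while the area stays the same. The size item, in turn, is banded, so real shrinkage inside a band is not registered.

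Two errors could follow. A difference in PUSH totals could be reported as faster closure when the wounds are cleaner and drier but no smaller. Or a true difference in closure could be diluted by variation in the other items and by the banding. With 15 patients per arm there is little room for added noise.

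**Working it through.** **Inputs**

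- Maximum total 17: Appendix 2, healing graph.
- Tissue 0 to 4: Appendix 2, written scoring rules. A score of 0 is given only when the wound is closed.
- Exudate 0 to 3: an assumption of one point per level for the four named levels. The 0 to 5 column headings printed over these two items are set aside in favour of the written rules.
- Size bands in cm²: below 0.3 scores 1; 0.3–0.6 scores 2; 0.7–1.0 scores 3; 1.1–2.0 scores 4; 2.1–3.0 scores 5. Higher bands are not legible in the text available, so the size maximum comes by subtraction: 17 − 4 − 3 = 10. The figure of 17 therefore cannot be rebuilt independently.

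**Formula.** Fall in total = fall in size sub-score + fall in exudate + fall in tissue.

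| Change in the wound | Area reduction | Size | Exudate | Tissue | Fall in total |
|---|---|---|---|---|---|
| Necrotic, heavy exudate to granulating, dry | 0% | fixed | 3 to 0 | 4 to 2 | 5 |
| Same, but graded epithelial | 0% | fixed | 3 to 0 | 4 to 1 | 6 |
| Slough, moderate exudate to granulating, light | 0% | fixed | 2 to 1 | 3 to 2 | 2 |
| 2.0 to 1.1 cm² | 1 − 1.1/2.0 = 45% | 4 to 4 | fixed | fixed | 0 |
| 2.0 to 0.5 cm² | 1 − 0.5/2.0 = 75% | 4 to 2 | fixed | fixed | 2 |
| 2.0 to 0.25 cm² | 1 − 0.25/2.0 = 87.5% | 4 to 1 | fixed | fixed | 3 |

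**Relative size of the 5-point fall.** The total goes from 8 to 3 (5/8 = 62.5%) at size sub-score 1, from 11 to 6 (5/11 = 45%) at sub-score 4, and from 17 to 12 (5/17 = 29%) at sub-score 10. The milder 2-point fall is 6 to 4 (33%) at sub-score 1 and 15 to 13 (13%) at sub-score 10. On measured area, each of these wounds shows 0% closure.

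**Range for the exudate assumption.** If exudate contributes e points, the fall from necrotic to granulating is 2 + e. With e between 0 and 3, the range is 2 to 5. Even if exudate does not change at all, the fall of 2 equals that of a 75% area reduction with the other items fixed.

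**Cross-check with Section 6.h.** The analysis section expresses closure as reduction in wound size. Section 6.e departs from that by using a composite score for the same idea.

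**The case against.** The strongest reply is that exudate and tissue are not foreign to closure. Section 6.e defines complete closure by reepithelialization and absence of drainage; tissue grades 1 and 0 record the first, and an exudate grade of none the second. This stands. A reader might infer from (3 + 4)/17 = 41% that two-fifths of the score has nothing to do with closure. The documents do not support that, and not all 7 points can move in an open wound, since tissue 0 means closed. For the same reason the 6-point case is less clean than the 5-point case.

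A reader might also equate the 5-point fall with full closure of a 2.1–3.0 cm² ulcer, because its size sub-score falls from 5 to 0. On the total the two differ. Starting necrotic with heavy exudate, the ulcer that closes dry goes from 12 to 0; the one that stays open at the same area goes from 12 to 7.

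Nor do the documents show that debridement biases the comparison. It is given in both arms, and Section 6.b already requires it for entry, so the necrotic, heavily draining baseline is a worst case of unknown frequency. Appendix 2 does not say whether tissue is graded before or after debridement at a visit, but that too is mainly a source of noise. The control arm has no placebo and no masked assessor is described, so ratings could differ by arm. That is a separate weakness.

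Lastly, Section 6.e says scores rather than total scores, names photographs, and the recording form keeps sub-scores. This softens the point but does not remove it: no text selects the size item, the size item is itself banded, and the photographs have no measurement rule.

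**Conclusion.** The concern holds as one of construct and precision. Used as the tool directs, the PUSH total is a score of wound condition, which suits the healing assessment in Specific Aim 1, but it is a coarse, noisy measure of closure. An open wound of unchanged area can fall 5 points, while one that has lost 87.5% of its area (2.0 to 0.25 cm²) falls 3, and one that has lost 45% (2.0 to 1.1 cm²) falls 0, with the other items unchanged.

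This rests on the total being the score compared and on exudate scoring 0 to 3; under the range shown, the 5 becomes 2 to 5. The effect is mainly noise and a misleading label. Between-arm bias arises only if exudate or tissue ratings differ by arm for reasons other than closure. The primary outcome, complete closure at 6 weeks, does not use the PUSH total and is unaffected. The plan should be changed, but the matter is confined to a secondary outcome of a 30-patient pilot.

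**What to change.** - **Section 6.e:** define rate of wound closure as percent change from baseline in measured length × width (cm²) at weeks 2, 4 and 6.
- **Recording:** enter the raw cm² at baseline and at each of these visits beside the size sub-score. The ruler measurement is already part of the tool, but the form asks for sub-scores.
- **Section 6.h:** analyse rate of closure as a continuous repeated measure. Keep Cox regression for time to complete healing.
- **Reporting:** present PUSH total, exudate and tissue type separately as wound-condition outcomes, and do not describe a change in them as closure.

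The cost is one more recorded field, a small rewrite of Sections 6.e and 6.h, and possibly a less favourable secondary result than the PUSH total would give. The change does not cure unmasked assessment if the same provider takes the ruler measurement.

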## Pressure Ulcer Healing Chart

To monitor trends in PUSH Scores over time

(Use a separate page for each pressure ulcer)

Patient Name \_\_\_\_\_ Patient ID# \_\_\_\_\_

Ulcer Location \_\_\_\_\_ Date \_\_\_\_\_

### Directions:

Observe and measure pressure ulcers at regular intervals using the PUSH Tool.

Date and record PUSH Sub-scores and Total Scores on the Pressure Ulcer Healing Record below.

Pressure Ulcer Healing Record											
Date											
Length x Width											
Exudate Amount											
Tissue Type											
PUSH Total Score											

Graph the PUSH Total Scores on the Pressure Ulcer Healing Graph below.

PUSH Total Score	Pressure Ulcer Healing Graph											
17												
16												
15												
14												
13												
12												
11												
10												
9												
8												
7												
6												
5												
4												
3												
2												
1												
Healed = 0												
Date												

[figure not shown]
### **Appendix 3: Biweekly Clinic Survey (Weeks 2, 4, 6)**

## **Effects of Supplemental Immunonutrition on Healing of Chronic Non-Healing Lower Extremity Ulcers in Diabetic Patients: Clinic Survey**

Name: \_\_\_\_\_ Date: \_\_\_\_\_

1. Which follow-up visit are you being seen for today?  
 2-week visit  
 4-week visit  
 6-week visit
2. Did you receive immunonutrition supplements (Omega-3 fatty acids, Vitamin C, L-Arginine)?  
 Yes (proceed to question 3) \_\_\_\_\_  
 No (proceed to question 4)
3. Have you experienced any difficulty taking the supplementation according to the instructions?  
 Yes, please explain: \_\_\_\_\_  
 No
4. Have you experienced any of the following symptoms since your surgery? Check all that apply:  

 Abdominal Pain	 Low Blood Pressure
 Heartburn	 Burping
 Nausea	 Taste Perversion
 Vomiting	 Constipation
 Diarrhea	 Gastrointestinal Disorder
 Headache	 Itchy Skin
 Insomnia	 Easy bleeding or bruising
 Rash	 Red, itchy welts
 Indigestion	 Other, please explain: _____
 Palpitations	_____
 Numbness	
 Bitter Taste	
5. Have you made any trips to Emergency Departments/Urgent Care Centers since your last visit related to your foot ulcer?  
 Yes, please explain: \_\_\_\_\_  
 No
6. Circle your current level of pain related to your foot ulcer on the scale below:

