- a. Patients randomized to receive the oral immunonutrition supplementation in addition to standard of care will complete a daily compliance log documenting their intake of the provided supplements.
- b. All patients will complete a weekly survey rating their pain score (VAS) and any symptoms/side effects experienced during their study participation.
- c. At the final visit, subjects randomized to receive the oral immunonutrition supplementation will complete a satisfaction survey in which they detail their thoughts on their treatment plan.

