**Visit 1: 2 Week Follow-up (First visit after completing 14 days of oral immunonutrition):**

- Provider documents characteristics of wound via PUSH Tool 3.0, captures clinical photos, obtains interval history, performs interval physical exam, and verifies and documents concomitant medications in the patient's chart.
- Provider visualizes and evaluates any additional wounds that are present and records characteristics in the patient's chart.
- Patient completes questionnaire in clinic (VAS, experienced symptoms since enrollment, review of supplement compliance).

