## **Appendix 4: Biweekly Phone Survey (Weeks 1, 3, 5)**

### **Effects of Supplemental Immunonutrition on Healing of Chronic Non-Healing Lower Extremity Ulcers in Diabetic Patients: Phone Survey**

- 1) **Intro:** "Hello (*Patient's Name*), this is (*research staff member's name*) calling from the office of \_\_\_\_\_ . I am calling regarding the research study you previously agreed to be enrolled in. Is now an okay time to speak?"
  1. **If No:** "Okay, when would be an acceptable time to call you back?"
  2. **If Yes:** *proceed to number 2*
- 2) **VAS Pain score:** "On a scale of 0-10, with 0 being no pain, and 10 being the worst pain possible, how would you rate your foot ulcer pain currently?"

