#### **If the subject is enrolled in the treatment arm (received oral immunonutrition supplementation), proceed with questions 3 and 4. If not, skip to question 5:**

- 3) **Verification of supplementation:** "Did you receive supplementation and instructions on how it should be taken?"
  1. **If No:** "May I ask why not?"
  2. **If Yes:** *proceed to number 3*
- 4) **Medication compliance:** "Have you been able to take the supplementation daily as instructed?"
  1. **If No:** "May I ask why not?"
  2. **If Yes:** *proceed to number 3*
- 5) **Experienced symptoms:**
  1. "Have you experienced any of the following symptoms during your participation in the study. Please answer yes or no to each"
    - Abdominal pain, heartburn, nausea, vomiting, diarrhea, headache, insomnia, rash, indigestion, palpitations, numbness, bitter taste, low blood pressure, burping, taste perversion, constipation, gastrointestinal disorder, itchy skin, easy bleeding or bruising, red itchy welts
    - "Have you experienced any other symptoms"
      - If yes:** "can you please explain?"
      - If no:** *proceed to number 5*
- 6) **Emergency Department / Urgent Care Visits:** "Since beginning this study, have you had any unscheduled office visits, or have you been to any emergency departments or urgent care centers related to your foot ulcer?"
  1. **If Yes:** "Can you please explain?"
  2. **If No:** *proceed to number 6*

"Thank you for your time (*Patient name*), I hope you have a good day."

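### The clinic symptom survey asks about symptoms since a surgery that the trial neither plans nor requires, so three of the six scheduled symptom surveys carry the wrong recall period

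*Combined protocol and SAP*

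**What the plan says.** Appendix 3 is the paper form that patients fill in at the week 2, 4 and 6 office visits. Its question 4 reads "Have you experienced any of the following symptoms since your surgery" and is followed by a list of symptoms to tick.

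Elsewhere the protocol ties the recall period to the study:

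- **Section 6.f, Visit 1:** "Patient completes questionnaire in clinic (VAS, experienced symptoms since enrollment, review of supplement compliance". Visits 2 and 3 and the office-visit entry in Appendix 1 give the same period.
- **Section 6.f, item 5:** the questionnaire covers "symptoms experienced during the treatment phase".
- **Section 2, Aim 2(b):** "All patients will complete a weekly survey rating their pain score (VAS) and any symptoms/side effects experienced during their study participation".
- **Appendix 4, question 5 (phone survey, weeks 1, 3 and 5):** "Have you experienced any of the following symptoms during your participation in the study".

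Surgery is not among the inclusion criteria in Section 6.b, nor part of either arm in Section 6.f item 4. Both arms receive debridement, dressings and offloading, with or without supplements. Surgery appears only as something that may happen: a monitored outcome (Sections 2, 6.h and 6.i), a circumstance for withdrawal when it is expected within the six weeks (6.k), and a contingency in the safety plan (9).

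**The concern.** The form is an instrument that patients will answer, so its wording determines what is recorded. A patient who has had no operation is given no start date. A patient who has had one is given a date that may have nothing to do with enrolment or the supplements.

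The layout makes this harder to detect. Question 4 is a list to tick, with an option for other symptoms but none for no symptoms. The phone script asks for yes or no on each symptom. On the clinic form, a patient who skips the item as irrelevant leaves the same record as a patient without symptoms.

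What is at stake is the symptom and side-effect information promised in Aim 2(b). It has some weight because Section 7 says that this combination has not been studied in humans and that its risks are unknown, and because the Data Safety Committee reviews accumulating adverse events after every five enrolments.

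**Working it through.** The plan states no figure on this point, so there is none to reproduce. The check is a comparison of wording, a count of forms, and a look at what else covers the same period.

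**1. Recall period by source**

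| Source | Start of recall |
|---|---|
| Appendix 3, question 4 (clinic form) | surgery |
| Section 6.f, Visits 1, 2 and 3 | enrolment |
| Appendix 1, office visits | enrolment |
| Section 6.f, item 5 | treatment phase |
| Section 2, Aim 2(b) | study participation |
| Appendix 4, question 5 (phone form) | study participation |

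The last five differ slightly in wording, but all are tied to the study. Only the clinic form is not.

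**2. Count of affected forms**

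- Clinic surveys per patient: 3 (weeks 2, 4, 6; Appendix 3).
- Phone surveys per patient: 3 (weeks 1, 3, 5; Appendix 4).
- Planned enrolment: 30, with 15 per arm (Section 6.c).
- Share with the surgical anchor: 3 / (3 + 3) = 50%.
- Forms, if every patient completes every contact: 3 × 30 = 90 of 6 × 30 = 180.
- With question 4 anchored to enrolment: 0 of 180.

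If the treatment arm's final safety follow-up is counted as a seventh contact, the share in that arm is 3 / 7 = 43%. That contact is a provider's review of adverse events with no symptom survey attached, so 3 of 6 is the better figure.

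**3. What else covers the same weeks**

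- The phone question covers the whole of participation to date, so the week 5 call reaches back over weeks 0 to 5.
- From week 5 to week 6, treated patients also have question 7 of the completion survey (Appendix 5), an open question on negative effects of the supplements. Controls do not complete that survey, so among patient surveys the clinic form is their only source for that week.
- At each office visit where the clinic form is used, the provider takes an interval history and performs an examination (Section 6.f).
- Section 9 records adverse events at visits, by phone and by chart review. It adds alerts for emergency visits and admissions, and daily chart review for the supplement arm.

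**4. Use in the analysis**

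No endpoint in Section 6.e and no regression model in Section 6.h is built on question 4. At most, its answers would enter the general summaries and unadjusted comparisons at the start of Section 6.h.

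**The case against.** The strongest reply is that this is a slip on one form with little consequence. Symptom capture is redundant, as step 3 of the working shows. Stopping the supplement depends on graded adverse events (Section 9), not on ticks on this form. The form also gives context: its title names the study, question 1 asks which follow-up visit this is, questions 2 and 3 concern the supplements, and question 5 refers to the period since the last visit. Many patients would work out what is meant.

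Most of this stands, and it limits the size of the point. It does not make the wording right: other sources do not repair a question whose period differs from the one the protocol sets for it.

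Three stronger readings are tempting, and the documents do not support them:

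- **That half of the safety data is lost or meaningless.** The 90 of 180 counts sheets of paper, not missed or misattributed symptoms. The documents give no basis for estimating those, and the survey is one of several routes.
- **That side effects will be biased in a known direction.** Both arms receive the form. A misread anchor could suppress reports in some patients and add old symptoms in others.
- **That surgery has no place in the trial.** It can occur unplanned and is monitored. The accurate statement is that none is planned or required.

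Nor would a new anchor make clinic and phone reports fully comparable. One is a self-completed tick list and the other is read out item by item, and the plan specifies no comparison between them.

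**Conclusion.** The point holds as an internal inconsistency of low severity. The clinic form uses a recall anchor that conflicts with the protocol's own definition for the same questionnaire, on 3 of 6 scheduled symptom surveys per patient. The total of up to 90 of 180 forms assumes full enrolment of 30 and completion of every contact.

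The consequence is confined to the quality and interpretability of survey-reported symptoms, mainly because blanks on the clinic form are ambiguous. That some patients will skip or misread the item is a risk inferred from the wording, not something the documents show. The primary endpoint of complete wound closure does not depend on this item and is unaffected.

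**What to change.** In Appendix 3, question 4, replace *since your surgery* with *since you enrolled in this study*, which matches the visit schedule in Section 6.f and Appendix 1. Submit the amended form to the IRB. If any clinic forms have already been completed with the present wording, flag their question 4 answers in the dataset so that they can be identified in any symptom summary.

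The same edit can correct a cross-reference: Section 6.f item 5 cites Appendix 4 for the clinic survey and Appendix 3 for the phone survey, the reverse of the appendix headings.

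The cost is one phrase on one form, its IRB handling, and a data flag if forms are already in use. No visit, endpoint, analysis or treatment rule changes.
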